8.2 Populations for Analyses

- All Enrolled subjects: All subjects who signed an informed consent form and were registered into the IWRS
- All Randomized subjects: All enrolled subjects who were randomized to any treatment arm. This is the primary dataset for analyses of study conduct, efficacy parameters, baseline characteristics [REDACTED]
- All Treated subjects: All randomized subjects who received at least one dose of study drug. This is the primary dataset for safety and exposure analyses.

8.3 Endpoints

8.3.1 Primary Endpoint

The primary objectives in the study will be measured by the primary endpoint of PFS assessed by investigator within the N-Pd and Pd arms.

8.3.1.1 Progression Free Survival

PFS is defined as the time from randomization to the date of the first documented tumor progression or death due to any cause. PFS will be determined by an investigator, based upon laboratory data (eg, SPEP/IFE, UPEP/IFE, bone marrow disease assessment, serum FLC) as defined by the IMWG criteria. Subjects who die without a reported prior progression will be considered to have progressed on the date of their death. Subjects who did not progress or die will be censored on the date of their last efficacy assessment. Subjects who did not have any on study efficacy assessments and did not die will be censored on the date they were randomized. Subjects who started any subsequent anti-cancer therapy without a prior reported progression will be censored at the last efficacy assessment prior to subsequent anti-cancer therapy.

8.3.2 Secondary Endpoint(s)

Overall Survival (OS)

OS is defined as the time between the date of randomization and the date of death due to any cause. OS will be censored on the last date a subject was known to be alive.

Objective Response Rate (ORR)

Objective response rate is defined as the proportion of randomized subjects who achieve a best overall response of stringent complete response (sCR), complete response (CR), very good partial response (VGPR), or partial response (PR) using the IMWG criteria.

Time to Response (TTR)

Time to Response (TTR) is defined as the time from the date of randomization to the date of the first sCR, CR, VGPR, or PR. TTR will be evaluated for responders (BOR is either sCR, CR, VGPR, or PR) only.

Duration of Response (DOR)

Duration of Response (DOR) is defined as the time between the date of first response to the date of the first objectively documented tumor progression as assessed by independent review committee according to modified IMWG criteria or death due to any cause prior to subsequent anti-cancer therapy. Subjects who neither progress nor die will be censored on the date of their last tumor assessment prior to subsequent anti-cancer therapy. DOR will be evaluated for responders (BOR is either sCR, CR, VGPR, or PR) only.

8.3.3 *Exploratory Endpoint(s)*

Within the NE-Pd arm, the following endpoints are considered as exploratory endpoints, ORR, PFS, DOR, and TTR by investigator.

For subjects who crossed-over from the control arm (Pd) to the exploratory arm (NE-Pd), the following endpoints are considered as exploratory efficacy endpoints, ORR, PFS, DOR, and TTR by investigator.

8.4 *Analyses*

The main analysis will be performed after the last subject has complete safety follow up (at least 100 days after study drug discontinuation).

8.4.1 *Demographics and Baseline Characteristics*

Demographic and baseline characteristics will be summarized for all randomized subjects by treatment group, as randomized, using descriptive statistics.

8.4.2 Efficacy Analyses

8.4.2.1 Methods for Primary Endpoints

PFS Analysis Time points

- At the time of PFS analyses, as assessed by investigator, the distribution of PFS in N-Pd group will be compared with the Pd via a two-sided, log-rank test stratified by prior lines of therapy and ISS stage at study entry. The hazard ratio (HR) and the corresponding 100x(1-adjusted alpha)% confidence interval (CI) will be estimated in a stratified Cox proportional hazards model using treatment as a single covariate.
- PFS curves, PFS medians with two-sided 95% CIs, and PFS rates at select milestone with 95% CIs will be estimated using Kaplan-Meier methodology.

8.4.2.2 Methods for Secondary Endpoints

Analysis of OS

- At the time of PFS analyses, OS will be summarized by the Kaplan-Meier product-limit method within each arm. Median values along with two-sided 95% CIs based on the log-log transformation, will be calculated. Additional details of OS analysis will be included in the SAP

Analysis of ORR by Investigator

- Investigator-determined ORR analyses will be conducted using a two-sided Cochran-Mantel-Haenszel (CMH) test stratified by prior lines of therapy and ISS stage at study entry to compare N-Pd to Pd arm. Associated odds ratios and 95% CIs will be calculated. Additionally, ORRs and corresponding 95% exact CIs will be calculated using the Clopper-Pearson method for N-Pd and Pd arms

Analysis of DOR and TTR

- DOR and TTR will be computed for subjects who achieve sCR, CR, VGPR, or PR as assessed by investigator according to modified IMWG criteria. Median values of DOR, along with two-sided 95% CI, will be calculated using KM product-limit method. Summary statistics of TTR will be provided. More detailed analysis of DOR and TTR will be described in the SAP

Details on the testing procedure will be described in SAP.

[figure not shown]
8.4.2.3 Methods for Exploratory Endpoints

[figure not shown]
Details of following analyses will be included in the SAP.

- Analyses of the data for subjects who crossed-over from the control arm (Pd) to the exploratory arm (NE-Pd) will be analyzed separately
- Analyses of the data in NE-Pd arm are of exploratory nature and may be performed at several times prior to completion of the study in order to facilitate program decisions

8.4.3 Safety Analyses

The safety analysis will be performed in all treated subjects. Descriptive statistics of safety will be presented using National Cancer Institute (NCI) Common Terminology Criteria for Adverse Events (CTCAE) version 4.0 by treatment group. Adverse Events (AE), drug-related AEs, Serious Adverse Events (SAE) and drug-related SAEs will be tabulated using worst grade per NCI CTCAE v.4.0 criteria by system organ class and preferred term. On-study lab parameters including hematology, chemistry, liver function and renal function will be summarized using worst grade per NCI CTCAE v.4.0 criteria.

8.4.7 *Other Analyses*

Not applicable

8.5 *Interim Analyses*

Interim Analysis for PFS Futility

At FDA's request on 21-June-2018, a formal PFS interim analysis for futility was conducted in August 2018 based on the database lock on 12-April-2018. The investigator assessed progression events (NPd and Pd arms) were used in this analysis. Prior to running the futility analysis, a futility criteria was defined based on conditional power assuming 85 events (30% information fraction). The stopping criteria for futility was that the conditional power under observed trend is strictly less than 1%. This would correspond to a HR (NPd vs. Pd) boundary of 0.995 and the corresponding conditional power under alternative would be 67.8%, ie if alternative hypothesis is true (HR = 0.667), there is still 67.8% chance that the study will be positive at the final analysis.

Subsequently, after conducting the interim analysis, the decision was made to permanently discontinue enrolment based on insufficient clinical benefit observed at an interim futility analysis for PFS. All futility analyses were conducted by the unblinded independent statistics vendor.

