Clinical Protocol CA209602

Protocol Title: An Open-Label, Randomized Phase 3 Trial of Combinations of Nivolumab, Pomalidomide and Dexamethasone in Relapsed and Refractory Multiple Myeloma

(CheckMate 602: CHECKpoint pathway and nivolumab clinical Trial Evaluation 602)

Investigational Product(s), Dose and Mode of Administration, Duration of Treatment with Investigational Product(s): See Study Schema for details

Control Arm (Pd: Arm B):

Pomalidomide: 4 mg PO QD Days 1-21 of each 28-day cycle

Dexamethasone:

- Subjects ≤ 75 years old: 40 mg PO Days (1, 8, 15, and 22) of each cycle
- Subjects > 75 years old: 20 mg PO Days (1, 8, 15, and 22) of each cycle

Investigational Arm (N-Pd: Arm A):

Nivolumab:

- Cycles 1 through 4: 240 mg IV Days 1, 15 of each 28-day cycle
- Cycles 5 and beyond: 480 mg IV Day 1 of each 28-day cycle

Pomalidomide: 4 mg PO QD Days 1-21 of each 28-day cycle

Dexamethasone:

- Subjects ≤ 75 years old: 40 mg PO Days (1, 8, 15, and 22) of each cycle
- Subjects > 75 years old: 20 mg PO Days (1, 8, 15, and 22) of each cycle

Exploratory Arm (NE-Pd: Arm C): Enrollment closed per Revised Protocol 02

Nivolumab:

- Cycles 1 through 4: 240 mg IV Days 1, 15 of each 28-day cycle
- Cycles 5 and beyond: 480 mg IV Day 1 of each 28-day cycle

Elotuzumab:

- Cycles 1 - 2: 10 mg/kg IV Days 1, 8, 15, and 22 of each 28-day cycle
- Cycle 3 and 4: 10mg/kg IV Day 1 and 15 of each 28-day cycle
- Cycles 5 and beyond: 20 mg/kg IV Day 1 of each 28-day cycle

Pomalidomide: 4 mg PO QD Days 1-21 of each 28-day cycle

Dexamethasone: Days 1, 8, 15, and 22 of each cycle

- Subjects ≤ 75 years old: weeks with elotuzumab dosing: 28 mg PO + 8 mg IV and 40 mg PO on non-elotuzumab dosing weeks
- Subjects > 75 years old: weeks with elotuzumab dosing: 8 mg PO + 8 mg IV and 20 mg PO on non-elotuzumab dosing weeks

A cycle is defined as 28 days. Treatment with study drug continues until disease progression, unacceptable toxicity, or subject meets other criteria for discontinuation of study drug outlined in [Section 3.5](#).

Study Phase: 3

Research Hypothesis: The addition of nivolumab to pomalidomide and dexamethasone will increase the clinical benefit represented by increased progression free survival (PFS) and higher response rate compared to pomalidomide and dexamethasone in subjects with relapsed and/or refractory multiple myeloma.

Objectives:

Primary Objectives

[figure not shown]

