Hazard ratio for progression-free survival was 0.70 (95% confidence interval, 0.57 to 0.85; P=0.0004). 1-year progression-free survival rate in the elotuzumab group was 68%, versus 57% in the control group; 2-year rate was 41% versus 27%. Median progression-free survival in the elotuzumab group was 19.4 months versus 14.9 months in the control group. Overall response rate in the elotuzumab group was 79% versus 66% in the control group (P=0.0002).

In the 635 treated subjects, adverse events of any grade occurred in 99% of patients. In the elotuzumab group, 34% of the patients experienced grade 3 to 4 neutropenia versus 44% in the control group; 77% versus 49% of patients had grade 3 to 4 lymphopenia, respectively. The most common non-hematologic toxicities (> 30% of patients) included infections, fatigue, pyrexia, diarrhea, constipation, and cough. The most common grade 3 to 4 non-hematologic toxicities were fatigue and pneumonia. In the elotuzumab group, infections were reported for 81% of patients versus 74% in the control group. When adjusted for the longer drug exposure in the elotuzumab group, infection rates were equal in both groups (incidence rate per 100 patient years, 197). Consequently, despite the higher rate of lymphopenia observed in the elotuzumab group, there were no apparent untoward clinical manifestations.

In the elotuzumab group, study drug toxicity was the primary cause of death in 5 (2%) patients versus 6 (2%) in the control group.

Thirty-five (6%) patients had a second primary malignancy: 22 (7%) in the elotuzumab group and 13 (4%) in the control group. The incidence rates of second hematologic malignancies were identical in the elotuzumab and control groups (2% in each group); rates of second solid tumors were 3% versus 2%, respectively, and rates of non-melanoma skin cancers were 3.1% versus 1.5%, respectively. When adjusted for exposure to study therapy, the incidence rates of second primary malignancies per 100 patient-years were similar at 3.5 versus 2.8, respectively.

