It is possible that unforeseen or unanticipated adverse events may occur. In order to minimize the overall risks to participating subjects, the protocol has inclusion-exclusion criteria appropriate to the population, and specific follow-up safety assessments. Adverse events and serious adverse events will be reviewed on an ongoing basis by the Medical Monitor and the Sponsor's pharmacovigilance group to look for trends and safety concerns. Additionally, to ensure subjects' safety, an independent Data Monitoring Committee (DMC) will also be established to monitor the

safety of subjects treated with the combination regimens regularly and identify any early safety signal.

Recent safety concerns of increased risk of mortality and severe adverse events have been reported from two studies with pembrolizumab, an anti-PD-1 monoclonal antibody not approved for treatment of multiple myeloma, in combination with IMiD (lenalidomide and pomalidomide) and dexamethasone (<https://www.fda.gov/Drugs/DrugSafety/ucm574305.htm>). In light of these safety concerns, on 1 September 2017 the FDA requested that CA209602 be placed on partial clinical hold. As a consequence, as of 1-September-2017, enrollment in this study was stopped, as well as the cross-over of subjects randomized to the Pd control arm into the exploratory NE-Pd arm. Subjects on treatment as of 1-September-2017 who were deriving clinical benefit can continue treatment and must be monitored as per protocol requirements. As of Revised Protocol 02, the exploratory NE-Pd arm is removed from the study design, and enrollment in the study is focused on the investigational (N-Pd) and control (Pd) arms.

At FDA request, an interim PFS futility analysis based on the 12- April- 2018 database lock was performed to compare PFS between NPd and Pd arms. Based on the results of this futility analysis, on 23-August-2018 Bristol-Myers Squibb (BMS) has decided to permanently discontinue enrollment into the study due to insufficient evidence. The number of deaths that have occurred in the Arm NEPd (50%) were higher compared to those in the Arm NPd (29%) and Arm Pd (23%).

Three additional subjects in Arm Pd who crossed over to Arm NE-Pd have died due to disease progression, resulting in a total of 19 (27%) deaths in Arm Pd.

Among all treated subjects, the rates of serious adverse events [SAE] were higher in patients in Arm N-Pd (58%) and Arm NE-Pd (63%) compared to patients in Arm Pd (50%).

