Sections 5.6.1 and 5.6.2 of the nivolumab and elotuzumab Investigator Brochure (IB) contains the Reference Safety Information to determine expectedness of serious adverse events for expedited reporting. Following the subject's written consent to participate in the study, all SAEs, whether related or not related to study drug, must be collected, including those thought to be associated with protocol-specified procedures. All SAEs must be collected that occur during the screening period and within 100 days of discontinuation of dosing or within 30 days of the last visit for screen failures. For subjects randomized and never treated with study drug, SAEs should be collected for 30 days from the date of randomization.

The investigator must report any SAE that occurs after these time periods and that is believed to be related to study drug or protocol-specified procedure.

The investigator must report any SAE that occurs after these time periods and that is believed to be related to study drug or protocol-specified procedure.

An SAE report must be completed for any event where doubt exists regarding its seriousness.

If the investigator believes that an SAE is not related to study drug, but is potentially related to the conditions of the study (such as withdrawal of previous therapy or a complication of a study procedure), the relationship must be specified in the narrative section of the SAE Report Form.

SAEs, whether related or not related to study drug, and pregnancies must be reported to BMS (or designee) within 24 hours of awareness of the event. SAEs must be recorded on the SAE Report Form; pregnancies on a Pregnancy Surveillance Form (electronic or paper forms). The preferred method for SAE data reporting collection is through the eCRF. The paper SAE/pregnancy surveillance forms are only intended as a back-up option when the eCRF system is not functioning. In this case, the paper forms are to be transmitted via email or confirmed facsimile (fax) transmission to:

SAE Email Address: Refer to Contact Information list.

SAE Facsimile Number: Refer to Contact Information list.

For studies capturing SAEs through electronic data capture (EDC), electronic submission is the required method for reporting. In the event the electronic system is unavailable for transmission, paper forms must be used and submitted immediately. When paper forms are used, the original paper forms are to remain on site.

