6.2.1 Nonserious Adverse Event Collection and Reporting

The collection of nonserious AE information should begin at initiation of study drug until 100 days from the last dose of study drug. Nonserious AE information should also be collected from the start of a placebo lead-in period or other observational period intended to establish a baseline status for the subjects.

Nonserious AEs should be followed to resolution or stabilization, or reported as SAEs if they become serious (see [Section 6.1.1](#)). Follow-up is also required for nonserious AEs that cause interruption or discontinuation of study drug and for those present at the end of study treatment as appropriate. All identified nonserious AEs must be recorded and described on the nonserious AE page of the CRF (paper or electronic).

Completion of supplemental CRFs may be requested for AEs and/or laboratory abnormalities that are reported/identified during the course of the study.

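### Adverse events are summarised only as crude worst-grade percentages by arm, although time at risk can differ between arms; exposure-adjusted rates should stand beside them

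*Combined protocol and SAP*

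**What the plan says.** Section 8.4.3 sets the population and the form of the safety analysis. "The safety analysis will be performed in all treated subjects", with descriptive statistics by treatment group, and "Adverse Events (AE), drug-related AEs, Serious Adverse Events (SAE) and drug-related SAEs will be tabulated using worst grade per NCI CTCAE v.4.0 criteria", broken down by system organ class and preferred term. It names no patient-years, incidence rate or time-to-first-event analysis. Section 8.4.7 (Other Analyses) is marked not applicable.

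Section 8.2 says of the treated set: "This is the primary dataset for safety and exposure analyses". It gives no method for the exposure analyses and does not link them to adverse event rates.

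The observation period is not fixed. The Synopsis states: "Treatment with study drug continues until disease progression, unacceptable toxicity, or subject meets other criteria for discontinuation of study drug". For nonserious events, section 6.2.1 states: "The collection of nonserious AE information should begin at initiation of study drug until 100 days from the last dose of study drug". For serious events, section 6.1.1 states: "All SAEs must be collected that occur during the screening period and within 100 days of discontinuation of dosing".

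Section 1.7 already reads crude proportions side by side: "the rates of serious adverse events [SAE] were higher in patients in Arm N-Pd (58%) and Arm NE-Pd (63"%), against 50% on Pd.

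**The concern.** A worst-grade table answers one question: what share of subjects had the event while they were being watched. If one arm is watched longer, its share rises even when the event rate is the same. If one arm stops treatment sooner, its share falls and a higher rate can go unseen.

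The protocol itself shows the effect. Section 1.3.2 reports infections in 81% versus 74% of subjects in the elotuzumab phase 3 trial, then adds: "When adjusted for the longer drug exposure in the elotuzumab group, infection rates were equal in both groups (incidence rate per 100 patient years, 197"). The protocol relies on that adjustment to draw a reassuring conclusion about another trial, but does not plan it for this one.

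The stake is real here. The study went through a partial clinical hold over mortality and severe adverse events with another PD-1 inhibitor, and enrolment then closed after a futility analysis. Readers of the final report will look closely at toxicity, and the N-Pd versus Pd SAE contrast is the figure they will take from it.

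**Working it through.** **Design figure first.** Section 8.4.3 states no figure of its own. The medians used below come from section 8.1: 6 versus 4 months, HR 4/6 = 0.667, 262 PFS events, 90% power, two-sided 5%. These reproduce. Schoenfeld's formula gives 257 events for a fixed design, and 262 events with the two-look O'Brien-Fleming-type boundary give 90.2% power.

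**Inputs from the documents.** SAE proportions 58% (N-Pd) and 50% (Pd), section 1.7. Collection window of 100 days after the last dose, sections 6.1.1 and 6.2.1; 100/30.4375 = 3.29 months. Arms of 75 and 71 randomized subjects, section 3.1.

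**Assumptions, not in the documents.** Time on treatment is exponential. The Pd median is 4 months (design median PFS used as a stand-in for treatment time). The SAE hazard is constant. Death within the 100-day window is ignored.

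**Formula.** With h = ln 2/median, F = 3.29 months and SAE hazard λ, the crude incidence is 1 − [h/(h+λ)]·exp(−λF).

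**Step 1: calibrate Pd.** With h = 0.1733 (median 4), an incidence of 50% requires λ = 0.0871 per month. Check: 0.1733/0.2604 = 0.6656; exp(−0.0871 × 3.285) = 0.7512; 1 − 0.6656 × 0.7512 = 0.500.

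**Step 2: same hazard on N-Pd, longer treatment.** At a median of 6 months, h = 0.1155 and h/(h+λ) = 0.5702, so the incidence is 1 − 0.5702 × 0.7512 = 57.2%. Mean time at risk is 6/ln 2 + 3.29 = 11.9 months versus 4/ln 2 + 3.29 = 9.1 months, a ratio of 1.32. At a median of 4.5 months the incidence is 52.0%.

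**Step 3: vary N-Pd exposure, Pd fixed at 4 months.**

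| N-Pd median (months) | N-Pd incidence if hazards are equal | Hazard ratio implied by 58% vs 50% |
|---|---|---|
| 2 | 40.0% | 1.76 |
| 3 | 45.4% | 1.48 |
| 4 | 50.0% | 1.29 |
| 5 | 53.9% | 1.14 |
| 6 | 57.2% | 1.03 |

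In the hiding direction, equal crude incidences of 50% would conceal hazard ratios of 1.16 and 1.38 at N-Pd medians of 3 and 2 months.

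**Step 4: does the adjusted rate remove the artefact?** In a simulation with the same hazard in both arms and medians of 6 and 4 months (2 million subjects per arm), crude incidence was 57.1% versus 50.0%. First events per 100 patient-years at risk were 104.4 versus 104.6, a ratio of 1.00.

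**Step 5: sampling error of the reported gap.** SE = √(0.58 × 0.42/75 + 0.50 × 0.50/71) = 0.0823. The 95% CI is 0.08 ± 1.96 × 0.0823, about −8 to +24 points. It uses randomized arm sizes because the treated numbers are not given.

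**The case against.** The strongest reply is that the bias may be small in this trial. The 6 versus 4 month medians describe success. Enrolment closed for insufficient benefit on PFS, with a futility boundary at HR 0.995 (section 8.5), so a large N-Pd exposure advantage is unlikely. The elotuzumab trial differs too: it had a PFS benefit (HR 0.70) and 17 versus 12 months of treatment. This stands, and it is why the size is given as a range that includes almost no artefact. It does not remove the point, because shorter N-Pd treatment would make the crude tables understate toxicity.

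A second reply is that the tables are descriptive, no between-arm safety test is planned, and crude incidence is a legitimate summary. That also stands, and the crude tables should stay. But section 1.7 shows that the percentages are read as a contrast.

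Third, the protocol refers to a separate SAP, and section 8.2 mentions exposure analyses. No SAP text is available here, and it could close the gap. Section 8.4.3, however, does not defer to it, as the OS, DOR/TTR and crossover paragraphs do.

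Two stronger readings are tempting. One is that exposure explains the 58% versus 50%. A shortcut suggests that 25% more time at risk is enough: ln(0.42)/ln(0.50) = 1.25. That treats every subject in an arm as followed equally long. Under the model above, 58% needs a mean time ratio of about 1.36 (N-Pd median about 6.3 months), slightly beyond the design's own 1.32. The other reading is that the gap shows N-Pd to be more toxic. The documents support neither: they give no exposure by arm, and the interval for the gap includes zero. The 58% and 50% are also narrative figures reported with the interim results, not output of section 8.4.3. Some subjects may still have been on treatment, so the model is only illustrative for them.

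**Conclusion.** The point holds as a cheap improvement, not as an error that invalidates the safety analysis. Time at risk can differ between arms, and the planned tables cannot show whether it did. On the stated assumptions, the same 58% versus 50% is compatible with anything from almost no excess SAE hazard (1.03) to a 76% excess (1.76), depending on an N-Pd exposure that the documents do not report. With equal exposure at a 4-month median, the implied ratio is 1.29.

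The documents do not establish that exposure differs, in which direction, or that any reported difference is an artefact. The figures rest on a constant hazard and on PFS medians standing in for treatment time. Events that cluster early in treatment would be less sensitive to exposure than shown.

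**What to change.** Keep the crude worst-grade tables and add to section 8.4.3:

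- patient-years at risk by arm, from first dose to 100 days after the last dose, with the handling of death and first event stated;
- exposure-adjusted incidence rates per 100 patient-years for any AE, Grade 3-4 AEs, SAEs and drug-related SAEs;
- the N-Pd versus Pd rate ratio with 95% CI for each of these;
- cumulative incidence of first SAE by arm, with death as a competing event.

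Add a rule for Pd subjects who crossed over to NE-Pd: Pd time at risk and event counting end at the first NE-Pd dose, and later events are reported separately. This is consistent with section 8.4.2.3, which already has crossover data analysed separately. Without such a rule, NE-Pd time or events could be counted under Pd.

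The cost is a few extra tables and one figure from dosing and adverse event data already collected; no new visits are needed. The limitation is that a single rate assumes a constant hazard, so the rates must be read beside the cumulative-incidence curves. If exposure proves similar in the two arms, the additions will show that the crude contrast was fair.
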